12.5.2 PK/PD relationships

Data from this study may be used with pharmacokinetics/pharmacodynamics (PK/PD) models developed based on the core study CCFZ533B2201. This will be reported separately, if applicable.

12.5.3 Immunogenicity

All the results for immunogenicity data (anti-iscalimab antibodies) will be listed by visit/time.

If appropriate, summary statistics and shift tables will also be presented.

[REDACTED]

12.7 Interim analyses

Not applicable.

12.8 Sample size calculation

It is estimated that approximately 160 participants enrolled in the core study will complete the core study and be eligible for entry into the extension study.

13 Ethical considerations and administrative procedures

13.1 Regulatory and ethical compliance

This clinical study was designed and shall be implemented, executed and reported in accordance with the ICH Harmonized Tripartite Guidelines for Good Clinical Practice, with applicable local regulations (including European Directive 2001/20/EC, US CFR 21), and with the ethical principles laid down in the Declaration of Helsinki.

13.2 Responsibilities of the investigator and IRB/IEC

Before initiating a trial, the investigator/institution must obtain approval/favorable opinion from the Institutional Review Board/Independent Ethics Committee (IRB/IEC) for the trial protocol, written informed consent form, consent form updates, participant recruitment procedures (e.g., advertisements) and any other written information to be provided to participants. Prior to study start, the investigator is required to sign a protocol signature page confirming his/her agreement to conduct the study in accordance with these documents and all of the instructions and procedures found in this protocol and to give access to all relevant data and records to Novartis monitor, auditors, Novartis Quality Assurance representatives designated agents of Novartis, IRBs/IECs, and regulatory authorities as required. If an inspection of the clinical site is requested by a regulatory authority, the investigator must inform Novartis immediately that this request has been made.

13.3 Publication of study protocol and results

The protocol will be registered in a publicly accessible database such as clinicaltrials.gov and as required in EudraCT. In addition, after study completion and finalization of the study report the results of this trial will be submitted for publication and posted in a publicly accessible database of clinical trial results, such as the Novartis clinical trial results website and all required Health Authority websites (e.g., Clinicaltrials.gov, EudraCT etc.).

For details on the publication policy including authorship criteria, please refer to the publication policy training materials that were provided to you at the trial investigator meetings.

13.4 Quality Control and Quality Assurance

Novartis maintains a robust Quality Management System (QMS) that includes all activities involved in quality assurance and quality control, to ensure compliance with written Standard Operating Procedures as well as applicable global/local GCP regulations and ICH Guidelines.

Audits of investigator sites, vendors, and Novartis systems are performed by auditors, independent from those involved in conducting, monitoring or performing quality control of the clinical trial. The clinical audit process uses a knowledge/risk based approach.

Audits are conducted to assess GCP compliance with global and local regulatory requirements, protocols and internal SOPs, and are performed according to written Novartis processes.

14 Protocol adherence

This protocol defines the study objectives, the study procedures and the data to be collected on study participants. Additional assessments required to ensure safety of participants should be administered as deemed necessary on a case by case basis. Under no circumstances including incidental collection is an investigator allowed to collect additional data or conduct any additional procedures for any purpose involving any investigational drugs under the protocol, other than the purpose of the study. If despite this interdiction prohibition, data, information, observation would be incidentally collected, the investigator shall immediately disclose it to Novartis and not use it for any purpose other than the study, except for the appropriate monitoring on study participants.

Investigators ascertain they will apply due diligence to avoid protocol deviations. If an investigator feels a protocol deviation would improve the conduct of the study this must be considered a protocol amendment, and unless such an amendment is agreed upon by Novartis and approved by the IRB/IEC and Health Authorities, where required, it cannot be implemented.

16.1 Appendix 1: Clinically notable laboratory values and vital signs

The following criteria will be used to define expanded limits and notable abnormalities of key laboratory tests.

Table 16-1 Clinically notable laboratory values and vital signs

Laboratory variable	Standard units	SI units
Liver function and related variables		
SGOT (AST)	≥ 3 × ULN	≥ 3 × ULN
SGPT (ALT)	≥ 3 × ULN	≥ 3 × ULN
Bilirubin	≥ 3 × ULN	≥ 3 × ULN
Alkaline phosphatase	≥ 5 × ULN	≥ 5 × ULN
GGT	≥ 5 × ULN	≥ 5 × ULN
Renal function, metabolic and electrolyte variables		
Urea	≥ 5 × ULN	≥ 5 × ULN
Creatinine	≥ 3 mg/dL	≥ 265 μmol/L
Uric acid	M ≥ 12 mg/dL	M ≥ 714 μmol/L
	F ≥ 9 mg/dL	F ≥ 535 μmol/L
Glucose	< 45 mg/dL	< 2.5 mmol/L
	> 250 mg/dL	> 13.9 mmol/L
Cholesterol	≥ 350 mg/dL	≥ 9.1 mmol/L
Triglycerides	≥ 750 mg/dL	≥ 8.5 mmol/L
CK (MB)	None	None
Potassium	≤ 3.0 mEq/L	≤ 3 mmol/L
	≥ 6.0 mEq/L	≥ 6 mmol/L
Calcium	≤ 6 mg/dL	≤ 1.5 mmol/L
	≥ 13 mg/dL	≥ 3.2 mmol/L
Magnesium	< 1.0 mg/dL	< 0.4 mmol/L
	> 3.6 mg/dL	> 1.5 mmol/L
Amylase	≥ 2 x ULN	≥ 2 x ULN
Lipase	≥ 2 x ULN	≥ 2 x ULN
Hematology variables		
Hemoglobin	< 7 g/dL	< 4.39 mmol/L
Platelets (thrombocytes)	< 50 k/mm ³	< 50 × 10 ⁹ /L
	≥ 700 k/mm ³	≥ 700 × 10 ⁹ /L
Leukocytes (WBCs)	≤ 2.0 k/mm ³	≤ 2.0 × 10 ⁹ /L
	≥ 16 k/mm ³	≥ 16 × 10 ⁹ /L
Hematology variables: Differential		

Laboratory variable Liver function and related variables	Standard units	SI units
Granulocytes (poly, neutrophils)	≤ 1,000/mm ³	≤ 1 × 10 ⁹ /L
Eosinophils	≥ 12%	≥ 12%
Lymphocytes	≤ 1,000/mm ³	≤ 1 × 10 ⁹ /L
Vital sign variables	Notable criteria	
Systolic BP (mm/Hg)	Either an increase of ≥ 30 that results in ≥ 180 or > 200 (mm/Hg) OR a decrease of ≥30 that results in ≤ 90 or < 75 (mm/Hg)	
Diastolic BP (mm/Hg)	Either an increase of ≥ 20 that results in ≥ 105 or > 115(mm/Hg) OR a decrease of ≥20 that results in ≤ 50 or < 40 (mm/Hg)	

16.2 Appendix 2: Liver event and laboratory trigger definitions & follow-up requirements

Table 16-2 Liver event and laboratory trigger definitions

LIVER LABORATORY TRIGGERS LIVER EVENTS
	
Definition/ threshold
 
 • 3 x ULN < ALT / AST ≤ 5 x ULN • 1.5 x ULN < TBL ≤ 2 x ULN • ALT or AST > 5 x ULN • ALP > 2 x ULN (in the absence of known bone pathology) • TBL > 2 x ULN (in the absence of known Gilbert syndrome) • ALT or AST > 3 x ULN and INR > 1.5 • Potential Hy's Law cases (defined as ALT or AST > 3 x ULN and TBL > 2 x ULN [mainly conjugated fraction] without notable increase in ALP to > 2 x ULN) • Any clinical event of jaundice (or equivalent term) • ALT or AST > 3 x ULN accompanied by (general) malaise, fatigue, abdominal pain, nausea, or vomiting, or rash with eosinophilia • Any adverse event potentially indicative of a liver toxicity*

*These events cover the following: Hepatic failure, fibrosis and cirrhosis, and other liver damage-related conditions; the non-infectious hepatitis; the benign, malignant and unspecified liver neoplasms TBL: total bilirubin; ULN: upper limit of normal
	

Table 16-3 Follow up requirements for liver events and laboratory triggers

Criteria	Actions required	Follow-up monitoring

Potential Hy's Law case^a
	
 • Discontinue the study treatment immediately Hospitalize, if clinically appropriate • Establish causality • Record the AE and contributing factors (e.g., conmeds, med hx, lab) in the appropriate CRF 	
ALT, AST, TBL, Alb, PT/INR, ALP and GGT until resolution^c (frequency at investigator discretion)

ALT or AST > 8 x ULN
	
 • Discontinue the study treatment immediately • Hospitalize if clinically appropriate • Establish causality • Record the AE and contributing factors (e.g., 	
ALT, AST, TBL, Alb, PT/INR, ALP and GGT until resolution^c (frequency at investigator discretion)

Criteria	Actions required	Follow-up monitoring
	conmeds, med hx, lab) in the appropriate CRF	
> 3 × ULN and INR > 1.5	
 Discontinue the study treatment immediately Hospitalize, if clinically appropriate Establish causality Record the AE and contributing factors (e.g. conmeds, med hx, lab) in the appropriate CRF 	ALT, AST, TBL, Alb, PT/INR, ALP and GGT until resolution ^c (frequency at investigator discretion)
> 5 to ≤ 8 × ULN	
 Repeat LFT within 48 hours If elevation persists, continue follow-up monitoring If elevation persists for more than 2 weeks, discontinue the study drug Establish causality Record the AE and contributing factors (e.g., conmeds, med hx, lab) in the appropriate CRF 	ALT, AST, TBL, Alb, PT/INR, ALP and GGT until resolution ^c (frequency at investigator discretion)
> 3 × ULN accompanied by symptoms ^b	
 Discontinue the study treatment immediately Hospitalize if clinically appropriate Establish causality Record the AE and contributing factors (e.g., conmeds, med hx, lab) in the appropriate CRF 	ALT, AST, TBL, Alb, PT/INR, ALP and GGT until resolution ^c (frequency at investigator discretion)
> 3 to ≤ 5 × ULN (patient is asymptomatic)	
 Repeat LFT within the next week If elevation is confirmed, initiate close observation of the patient 	Investigator discretion Monitor LFT within 1 to 4 weeks
ALP (isolated) > 2 × ULN (in the absence of known bone pathology)	
 Repeat LFT within 48 hours If elevation persists, establish causality Record the AE and contributing factors (e.g., 	Investigator discretion Monitor LFT within 1 to 4 weeks or at next visit

Criteria	Actions required	Follow-up monitoring
	
conmeds, med hx, lab) in the appropriate CRF
	

TBL (isolated) > 2 × ULN (in the absence of known Gilbert syndrome)
	
 • Repeat LFT within 48 hours • If elevation persists, discontinue the study drug immediately • Hospitalize if clinically appropriate • Establish causality • Record the AE and contributing factors (e.g., conmeds, med hx, lab) in the appropriate CRF 	
ALT, AST, TBL, Alb, PT/INR, ALP and GGT until resolution^c (frequency at investigator discretion)
 
Test for hemolysis (e.g. reticulocytes, haptoglobin, unconjugated [indirect] bilirubin)

> 1.5 to ≤ 2 × ULN (patient is asymptomatic)
	
 • Repeat LFT within the next week • If elevation is confirmed, initiate close observation of the patient 	
Investigator discretion
 
Monitor LFT within 1 to 4 weeks or at next visit


Jaundice
	
 • Discontinue the study treatment immediately • Hospitalize the patient • Establish causality • Record the AE and contributing factors (e.g., conmeds, med hx, lab) in the appropriate CRF 	
ALT, AST, TBL, Alb, PT/INR, ALP and GGT until resolution^c (frequency at investigator discretion)

Any AE potentially indicative of a liver toxicity*
	
 • Consider study treatment interruption or discontinuation • Hospitalization if clinically appropriate • Establish causality • Record the AE and contributing factors (e.g. conmeds, med hx, lab) in the appropriate CRF 	
Investigator discretion

*These events cover the following: Hepatic failure, fibrosis and cirrhosis, and other liver damage-related conditions; the non-infectious hepatitis; the benign, malignant and unspecified liver neoplasms
TBL: total bilirubin; ULN: upper limit of normal.

^aElevated ALT/AST > 3 × ULN and TBL > 2 × ULN but without notable increase in ALP to > 2 × ULN ^b(General) malaise, fatigue, abdominal pain, nausea, or vomiting, or rash with eosinophilia ^cResolution is defined as an outcome of one of the following: (1) return to baseline values, (2) stable values at three subsequent monitoring visits at least 2 weeks apart, (3) remain at elevated level after a maximum of 6 months, (4) liver transplantation, and (5) death. *Based on investigator's discretion investigation(s) for contributing factors for the liver event can include: Serology tests, imaging and pathology assessments, hepatologist's consultancy; obtaining more detailed history of symptoms and prior or concurrent diseases, history of concomitant drug use, exclusion of underlying liver disease.*

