^X Assessment to be recorded in the clinical database or received electronically from a vendor

¹ Corresponds to the Week 60 visit of the core study. Assessments carried out as part of Week 60 as per core study protocol should be used for Week 60E1 of the extension study.

² Optional site visits - Week 66, 70, 74, 78, 82, 86, 90, 94, 98, 102, 106. Participants who are unable to self-administer the PFS injections at home will visit the site and site staff will supervise self-administration or administer the PFS injection for them. Other participants who can self-administer the PFS injection can do so at home at these optional visits.

³ Informed consent should be obtained before commencement of the Week 60 assessments of the core study.

⁴ Contact IRT for new treatment reassignment.

⁵ AEs/SAEs occurring after the participant has signed the informed consent must be captured on the appropriate eCRF page.

⁶ C - These assessments shall be conducted as part of the core study CCFZ533B2201 and will not be repeated in this extension study

⁷ S - Assessment to be recorded in the source documentation only

⁸ [REDACTED]

⁹ Local lab testing of CMV IgG, IgM and DNA (by PCR) must be performed every 3 months until end of study. Hepatitis B monitoring applicable to HBsAg (-) patients who were HBcAb (+) and HBV DNA (-) at screening during the core study. Local lab testing of HBsAg and HBV DNA must be performed every 3 months until end of study.

¹⁰ While on treatment, coagulation monitoring applies only to participants who have antiphospholipid antibodies (lupus anticoagulant, anti-cardiolipin antibodies) and/or who are on pre-existing antithrombotic therapy/prophylaxis, as reflected in the exclusion criteria of the TWINSS core study protocol.

¹¹ Analysis of cryoglobulins will be done only for participants who were positive at screening in the TWINSS core study.

¹² Urine pregnancy tests will be performed throughout the study

¹³ Blood sample is collected pre-dose.

¹⁴ [REDACTED]

¹⁵ [REDACTED]

¹⁶ Optional [REDACTED]

¹⁷ [REDACTED]

¹⁸ [REDACTED]

¹⁹ In case of premature discontinuation, participants will enter the follow-up after completing assessments for this visit.

²⁰ Mandatory to all participants, including those who have discontinued the study prematurely.

²¹ Week 106 is the last dose administration visit in the Treatment Period.

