10.2 Additional Safety Monitoring

10.2.1 Liver safety monitoring

There has been no safety signal for liver toxicity with iscalimab to date in all healthy volunteers and patients exposed, and from a mechanism of action standpoint there is no known effect on the liver (refer to the current Investigator's Brochure). Standard liver function tests (LFT) will be obtained at regular intervals.

The following two categories of abnormalities / adverse events have to be considered during the course of the study (irrespective of whether classified/reported as (S)AE):

- Liver laboratory triggers, which will require repeated assessments of the abnormal laboratory parameter
- Liver events, which will require close observation, follow-up monitoring and completion of the standard base liver CRF pages

Please refer to [Section 16.2](#) for complete definitions of liver laboratory triggers and liver events.

Every liver laboratory trigger or liver event as defined in [Section 16.2](#) should be followed up by the investigator or designated personnel at the trial site as summarized below. Detailed information is outlined in [Section 16.2](#).

For the liver laboratory trigger:

- Repeating the liver function test (LFT) within the next week to confirm elevation.

These LFT repeats must be performed using the central laboratory if possible. If this is not possible, then the repeats can be performed at a local laboratory to monitor the safety of the patient. Repeats laboratory must then be performed at central laboratory as soon as possible. If a liver event is subsequently reported, any local LFTs previously conducted that are associated with this event must be reported on the Liver CRF pages.

- If the elevation is confirmed, close observation of the patient will be initiated, including consideration of treatment interruption if deemed appropriate.

For the liver events:

- Repeating the LFT to confirm elevation as appropriate
- Discontinuation of the investigational drug if appropriate
- Hospitalization of the patient if appropriate

- A causality assessment of the liver event via exclusion of alternative causes (e.g., disease, co-medications)
- An investigation of the liver event which needs to be followed until resolution.

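### ALT/AST above 3 × ULN with INR above 1.5 mandates an immediate stop, yet no INR is required in response to an asymptomatic rise to between 3 and 5 × ULN

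*Protocol*

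**What the plan says.** Table 16-2 (Protocol, Appendix 2) lists "ALT or AST > 3 x ULN and INR > 1.5" among the liver events. The matching row of Table 16-3 says "Discontinue the study treatment immediately" and attaches no condition.

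The same tables treat ALT/AST above 3 and up to 5 × ULN on its own as a laboratory trigger. If the participant is asymptomatic, the row says "Repeat LFT within the next week", then close observation if the rise is confirmed. Follow-up is left to the investigator, with "Monitor LFT within 1 to 4 weeks". Section 10.2.1 matches this for a laboratory trigger: "Repeating the liver function test (LFT) within the next week to confirm elevation". It adds that close observation after confirmation includes considering treatment interruption.

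Table 8-3 lists INR only under Coagulation. Footnote 10 of Table 8-1 limits who gets that panel: "While on treatment, coagulation monitoring applies only to participants who have antiphospholipid antibodies", or who already take antithrombotic treatment. The blood log (Table 16-5) carries the same restriction.

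**The concern.** A mandatory participant-level stop rule has two inputs, an aminotransferase and an INR. The aminotransferase is measured in everyone. In the asymptomatic band between 3 and 5 × ULN, an INR above 1.5 would change the required action from repeat-and-observe, with interruption only to be considered, to immediate discontinuation. Yet no step taken in response to the trigger requires the INR.

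Two participants with the same ALT/AST and the same raised INR could thus be handled differently, one stopped and one still dosed, only because an INR happened to be drawn in the first.

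**Working it through.** The plan states no figure here to reproduce. The check compares the rules and counts scheduled draws.

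**1. Where PT/INR is requested.** Table 16-3 has 11 rows. Seven name it in follow-up, as "ALT, AST, TBL, Alb, PT/INR, ALP and GGT until resolution": potential Hy's Law, ALT/AST above 8 × ULN, above 3 × ULN with INR above 1.5, above 5 to 8 × ULN, above 3 × ULN with symptoms, isolated bilirubin above 2 × ULN, and jaundice. The asymptomatic row is one of the four that do not. In the row for above 5 to 8 × ULN the INR is expected, but its timing is left to the investigator.

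**2. Scheduled INR while dosing continues.** The source is Table 16-5. The last dose is at Week 106 (Table 8-1, footnote 21), so Week 108 is left out because no dose remains to be stopped.

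- Chemistry: Weeks 64, 68, 72, …, 104, which is (104 − 64)/4 + 1 = 11 visits.
- Coagulation panel at those visits: Weeks 72, 84 and 96, which is 3 visits.
- In the footnote-10 subset: 3 of 11 paired, 8 of 11 unpaired. The wait to the next panel is 8 weeks from Weeks 64, 76, 88 and 100, and 4 weeks from Weeks 68, 80, 92 and 104. From Weeks 100 and 104, that next panel (Week 108) falls after the last dose.
- Outside the subset: 0 of 11.

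Counting Week 108 as well would give 4 of 12 in the subset. Outside it the count would be 0 of 12, or 1 of 12 if Week 108 is read as off treatment.

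**3. Could an INR drawn with the repeat inform the next dose?** For a trigger at week w, the repeat is due by w + 1 and the next dose at w + 2. On nominal days the repeat comes first at all 11 visits. The visit windows in Section 8 weaken this:

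- Week 64 to Week 66, ±2 days each: shortest gap 14 − 2 − 2 = 10 days, longer than the 7 allowed for the repeat.
- From Week 68 on, ±5 days each: shortest gap 14 − 5 − 5 = 4 days, shorter than 7.

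So the order is guaranteed at 1 of 11 visits and is nominal at the other 10. Laboratory turnaround is not included.

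**4. Doses falling due before the next liver test.** If the repeat is done at w + 1 and the next liver test follows 1 to 4 weeks later, that test falls between w + 2 and w + 5. One dose (w + 2) or two (w + 2 and w + 4) fall due by then. After Week 104 only the Week 106 dose remains. That next test need not include an INR either.

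**The case against.** The strongest objection is that few participants would be in the gap. Under footnote b of Table 16-3, fatigue with ALT/AST above 3 × ULN leads to a row that stops treatment without needing an INR, and Section 1.1 says fatigue is among the features affecting nearly all patients with this disease. Neither table requires the symptom to be new, so the asymptomatic band may be small. This stands as a limit on size. It does not remove the gap, because the protocol keeps a separate asymptomatic row and so expects some participants in it.

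Second, the protocol never itemises LFT, and a site could read it to include INR. But Section 10.2.1 has standard liver tests taken at regular intervals in the study, whereas INR is not scheduled on treatment outside the subset, and Table 16-3 names PT/INR where it is wanted. At best the term is ambiguous.

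Third, other text gives room to act. Section 4.5 says in general terms that coagulation will be followed, but footnote 10 narrows this. Section 8.4.1 (discussion with the sponsor), Section 9.1.1 (stopping for any safety risk), Section 10.2.1 (considering interruption) and Section 14 (extra tests case by case) allow an INR. None requires one.

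A reader might infer that no INR is measured on treatment, so that this stop can never fire unless the investigator orders the test. The documents do not support that: the subset has scheduled panels at Weeks 72, 84 and 96. Nor do they support the inference that liver injury goes unwatched. Bilirubin and albumin are in every chemistry draw, and the Hy's Law, bilirubin and jaundice rows apply to everyone.

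**Conclusion.** The point holds for participants classed as asymptomatic with ALT/AST above 3 and up to 5 × ULN. Handled exactly as written, such a participant can meet a mandatory stop criterion without anyone knowing, unless the investigator orders an INR or, in the footnote-10 subset, a scheduled panel coincides. Scheduled coverage while dosing continues is 0 of 11 chemistry visits outside the subset and 3 of 11 inside it.

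The number of people affected cannot be computed. The documents give neither the subset's size, nor the number expected in this band, nor how often INR would exceed 1.5. Section 10.2.1 reports no liver signal to date, so it is likely to be small. The case for change is that the protocol's own stop rule should have its input and that supplying it is cheap, not that harm is expected to be common.

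The conclusion assumes that LFT does not include INR and that Table 16-5 gives the full coagulation schedule. A reader might also conclude that an INR added to the repeat would always be available before the next dose. The visit windows do not support that beyond Week 64.

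**What to change.** 1. In the asymptomatic row of Table 16-3 for ALT/AST above 3 and up to 5 × ULN, and in the laboratory-trigger bullet of Section 10.2.1, write: *Repeat LFT plus PT/INR within the next week, and before the next dose where feasible.*
2. In the same row's follow-up, write: *Monitor LFT and PT/INR within 1 to 4 weeks while ALT/AST remains > 3 × ULN.* Otherwise an INR that rises after the first repeat would still be missed.
3. Add to footnote 10 of Table 8-1, and to the matching footnote of Table 16-5: *This restriction does not apply to PT/INR drawn for a liver laboratory trigger or liver event.*

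Leave the INR criterion itself unchanged. Table 16-2 does carry exceptions for known bone disease (ALP) and Gilbert syndrome (bilirubin), but a similar exception for anticoagulant therapy would loosen an unconditional safety stop. That is a separate decision for the sponsor and is not needed to close this gap.

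The cost is one 1.8 mL coagulation tube per triggered draw, with the first added to a repeat that is already required, plus short text edits through an amendment approved under Section 14.1. The downside is an occasional stop for an INR rise that is not hepatic, including one due to anticoagulant therapy.

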8.4.1 Laboratory evaluations

Clinically notable laboratory findings are defined in [Section 16.1](#).

Clinically relevant deviations of laboratory test results occurring during or at completion of the study must be reported and discussed with Novartis personnel. The results should be evaluated for criteria defining an AE and reported as such if the criteria are met. Repeated evaluations are mandatory until normalization of the result(s) or until the change is no longer clinically relevant. In case of doubt, Novartis personnel should again be contacted.

In all cases, the Investigator must document in the source documents, the clinical considerations (i.e. result was/was not clinically significant and/or medically relevant) in allowing or disallowing the participant to continue in the study.

Clinically significant abnormalities must be recorded as either medical history/current medical conditions or adverse events as appropriate. All listed below laboratory evaluations will be performed by a central laboratory with exception of erythrocyte sedimentation rate (ESR), urinalysis, urine pregnancy test, cryoglobulins and hepatitis monitoring (HBsAg and HBV-DNA) applicable to HBsAg-negative, anti-HBc positive participants continuing from the TWINSS core study and CMV monitoring.

Table 8-3 Laboratory Evaluations

Test Category	Test Name
Hematology	Hematocrit, Hemoglobin, Platelets, Red blood cells, White blood cells, Differential (Basophils, Eosinophils, Lymphocytes, Monocytes, Neutrophils, Bands, Other), Erythrocyte sedimentation rate (ESR - local testing)
Chemistry	Albumin, Alkaline phosphatase, Alanine aminotransferase (ALT), Aspartate aminotransferase (AST), Gamma-glutamyl- transferase (GGT), Lactate dehydrogenase (LDH), Bicarbonate, Calcium, Magnesium, Phosphorus, Chloride, Sodium, Potassium, Creatinine, Direct Bilirubin, Indirect Bilirubin, Total Bilirubin, Total Cholesterol, Low Density Lipoprotein (LDL), High Density Lipoprotein (HDL), Total Protein, Triglycerides, Blood Urea Nitrogen (BUN) or Urea, Uric Acid, Amylase, Lipase, Glucose (non-fasting), C-reactive protein (CRP). Estimated creatinine clearance will be calculated using MDRD formula.

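### Table 16-3 requires a weaker action when ALT/AST, bilirubin and ALP are all raised than when bilirubin alone is raised

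*Protocol*

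**What the plan says.** Table 16-2 in Protocol Section 16.2 lists, among the liver events, "TBL > 2 x ULN (in the absence of known Gilbert syndrome"). ALP above 2 × ULN without known bone pathology is on the same list. Neither has to be an isolated finding.

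Table 16-3 gives the actions and adds that restriction to both rows: "TBL (isolated) > 2 × ULN (in the absence of known Gilbert syndrome") and "ALP (isolated) > 2 × ULN (in the absence of known bone pathology"). The word *isolated* is not defined. For the bilirubin row the instruction after a 48-hour repeat is "If elevation persists, discontinue the study drug immediately".

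The potential Hy's Law row requires an immediate stop, but footnote a limits it to cases without ALP above 2 × ULN. The two intermediate transaminase rows do not mention bilirubin. In the lower one, "> 3 to ≤ 5 × ULN (patient is asymptomatic"), the test is repeated within a week and a confirmed rise leads to close observation. In the one for above 5 and up to 8 × ULN, the test is repeated within 48 hours and then: "If elevation persists for more than 2 weeks, discontinue the study drug".

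**The concern.** Leaving ALP above 2 × ULN out of the potential Hy's Law row follows from how Hy's Law is defined and is not the fault. The fault is that no other row then picks up the raised bilirubin. A participant with three abnormal liver values can fall under a slower rule, or under no stopping rule, where bilirubin alone would have triggered a fixed one.

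What is at stake is the safety of individual participants. Chemistry is drawn about every four weeks while dosing is every two weeks (Table 16-5). The doses in between may be self-administered at home, so a clear rule tied to the laboratory result matters. No endpoint or analysis depends on this table.

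**Working it through.** **Inputs.** The rows and footnotes of Tables 16-2 and 16-3, Table 8-1 footnote 10 for INR availability, and the two-weekly dosing schedule. The rows for > 3 to ≤ 5 and > 5 to ≤ 8 × ULN carry no analyte label in the extracted text. They are read as ALT/AST rows, consistent with Table 16-2. No known Gilbert syndrome is assumed.

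**Step 1: which rows match?** Take ALT/AST > 3 to ≤ 8, TBL > 2 and ALP > 2 × ULN, with no listed symptoms, no jaundice, and INR ≤ 1.5 or unmeasured.

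| Table 16-3 row | Match? | Reason |
|---|---|---|
| Potential Hy's Law | No | ALP > 2 × ULN (footnote a) |
| ALT/AST > 8 | No | Below the threshold |
| ALT/AST > 3 with INR > 1.5 | No | INR condition not met |
| ALT/AST > 3 with symptoms | No | No symptoms |
| Jaundice | No | No jaundice |
| ALP isolated | No | TBL and ALT/AST also raised |
| TBL isolated | No | ALP and ALT/AST also raised |
| TBL > 1.5 to ≤ 2 | No | TBL > 2 |
| ALT/AST > 3 to ≤ 5, or > 5 to ≤ 8 | Yes | The only laboratory row left |

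**Step 2: compare the required actions.**

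| Pattern | Repeat | Stop |
|---|---|---|
| TBL > 2 alone | Within 48 hours | Immediately if persistent |
| All three raised, ALT/AST > 5 to ≤ 8 | Within 48 hours | Only if it persists more than 2 weeks |
| All three raised, ALT/AST > 3 to ≤ 5 | Within 1 week | No rule |

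The INR row is a limited safeguard. Table 8-1 footnote 10 says "While on treatment, coagulation monitoring applies only to participants who have antiphospholipid antibodies" or who are on antithrombotic therapy, and the > 3 to ≤ 5 row does not list PT/INR for follow-up.

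**Step 3: count the combinations.** Fix TBL > 2 and ALP > 2. Cross 4 ALT/AST bands (≤ 3, > 3 to ≤ 5, > 5 to ≤ 8, > 8) with symptoms, INR > 1.5 and jaundice (each yes or no): 4 × 2 × 2 × 2 = 32. Take the strictest matching row in each.

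- ALT/AST > 8 (8 combinations): always an immediate stop, so 0 are weaker.
- The two middle bands (8 each): symptoms, INR > 1.5 or jaundice each give an immediate stop. That leaves 1 weaker combination per band, 2 in total.
- ALT/AST ≤ 3 (8 combinations): if *isolated* means no ALT/AST elevation, the TBL row applies and 0 are weaker. If it means no other liver test is raised, only jaundice triggers a row. The 4 combinations without jaundice then match no laboratory row.

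Totals: 2 + 0 = **2 of 32**, or 2 + 4 = **6 of 32**. These are counts of logical cases, not probabilities.

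**Step 4: what the delay means in doses.** Assume doses on days 0, 14 and 28, and a result known on day x, with x from 1 to 11.

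- TBL rule: stop by day x + 2, that is day 3 to 13, before the day-14 dose. No further dose.
- > 5 to ≤ 8 rule: stop no earlier than day x + 15, that is day 16 to 26. One further dose.
- > 3 to ≤ 5 rule: no limit is set.

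**The case against.** The strongest reply is that *isolated* means only that no combined row higher in the table has already caught the case. Table 16-2 lists TBL > 2 × ULN as an event without qualification, and the TBL row is the one that implements it. On that reading the TBL row applies here and the count is 0 of 32. The reading strains the word: it calls bilirubin and ALP each isolated in someone in whom both, and ALT/AST, are raised. Nothing in the table points a site to it.

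Second, other sections still operate. Section 10.2.1 requires causality assessment and follow-up of every liver event. Section 8.4.1 requires discussion with the sponsor and says "Repeated evaluations are mandatory until normalization of the result(s) or until the change is no longer clinically relevant". Section 9.1.1 requires stopping where there may be a safety risk. All of this stands, so a stop remains possible. But it is a judged stop: Section 10.2.1 leaves discontinuation to what is appropriate.

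Third, the affected group is small. Fatigue is a listed symptom, and Section 1.1 describes it as affecting nearly all patients, so many might reach the symptom row. That holds only if pre-existing fatigue counts, which the table does not say. Section 10.2.1 also reports no liver signal to date.

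Fourth, the dose count holds only at nominal spacing. Visits from Week 68 may move by 5 days. With the next dose on day 9, a result on day 8 gives a TBL stop by day 10, possibly after that dose. With the next dose on day 19, results on days 1 to 3 allow a > 5 to ≤ 8 stop on days 16 to 18, before it. This objection is correct, but it affects only the illustration in doses and leaves the ordering of the rules unchanged.

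**Conclusion.** The concern holds. As written, Table 16-3 requires less for a worse liver pattern: 2 of 32 combinations under either literal reading of *isolated*, and 6 of 32 under the stricter one. For those 2, a stop about two days after the result becomes a stop after more than 14 days, or no stopping rule. At nominal dosing intervals and with the result known on days 1 to 11, the slower rule allows one more dose.

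The conclusion rests on taking *isolated* at its ordinary meaning, on the unlabelled rows being ALT/AST rows, and on no known Gilbert syndrome. The documents do not say how many participants would be affected; few is the reasonable expectation. The weakness is in the required action and does not prevent an investigator from stopping the drug.

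**What to change.** In Table 16-3, delete *isolated* from the TBL row. Alternatively, add a row for TBL > 2 × ULN together with ALP > 2 × ULN, with or without raised ALT/AST, at least as strict as the TBL row. Add one sentence saying that when several values are raised, the strictest matching row governs. If *isolated* stays in the ALP row, define it there.

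This is a wording change to one appendix table, by protocol amendment or a clarification to sites. It needs no new routine tests, because ALT, AST, bilirubin and ALP are already in the chemistry panel (Table 8-3). The cost is a few earlier repeat tests and possibly an earlier stop for a participant whose cholestatic pattern proves unrelated to the drug.
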